## **7.2 Method of Treatment Assignment**

All participants will be centrally assigned to treatment using an IRT. Before the study is initiated, each user will receive log in information and directions on how to access the IRT.

Enrolled participants, including those not dosed, will be assigned sequential participant numbers starting with 00001, (eg, 00001, 00002, 00003,... 00010). Those enrolled participants meeting inclusion and exclusion criteria will be eligible to be dosed. Sequential numbering may restart at 00001 for each participating site as the distinct patient identification number (PID) will ultimately be comprised of the site number and participant number, (eg, 0002 00001).

Once it is determined that the participant meets the eligibility criteria following the screening visit, the assigned treatment group and dose level will be provided by the site study team through the IRT prior to the first study treatment administration. The participant will be informed of one of the following:

- Assigned to Part 1 and which dose level in the monotherapy dose escalation portion of the study
- Assigned to Part 2 and which dose level in the combination dose escalation portion of the study
- Assigned to Part 3 and which biomarker category in the cohort expansion portion of the study
  - There should be a minimum of 5 participants per each selected indication in each cohort.

During dose escalation, all participants will be assigned to Part 1 until the decision is made to start combination dose escalation. If there are no openings available in the part to which the participant would be assigned by this algorithm, then the participant will be assigned to the next open part/cohort.

During monotherapy and combination dose escalation, participants who are not evaluable for DLT evaluation may be replaced. Replacement participants will be assigned to the same part (Part 1 or 2) and dose level, but will be assigned a new participant number. Please refer to the IRT manual for complete details on replacement of participants.

Participants in cohort expansion (Part 3) will be replaced if there is insufficient or unevaluable tumor tissue to determine CD8 level. The replacement participant will receive treatment as determined by CD8 TILs (see [Section 5.1.3](#)) and a new participant number will be assigned.

Study treatment will be dispensed at the study visits as listed in Schedule of Activities ([Section 2](#)).

### **7.3 Blinding**

Not applicable.

### **7.4 Dosage Modification**

#### **7.4.1 Dose-Limiting Toxicities**

For the purpose of guiding dose escalation, DLTs will be defined based on the incidence, intensity, and duration of AEs for which no clear alternative cause is identified. The DLT evaluation period will be 42 days (6 weeks). In the event of dose delays for reasons other than a potential DLT, the DLT evaluation period may be extended to include at least 28 days after the start of the sequential doses in Part 1 or at least 14 days after the start of Cycle 2 Day 1 sequential doses in Part 2. Participants requiring dose delays >7 days may be replaced for the purposes of DLT evaluation

but permitted to remain on study treatment unless permanent discontinuation criteria (Section 8.1) are met.

In all study parts, participants who complete the first cycle and do not have a DLT, have not had clinical evidence of disease progression, and are considered suitable for further treatment may receive up to 1 additional cycle of BMS-986277.

Additionally DLT's as defined below will require permanent discontinuation for all study participants regardless of treatment cycle.

In Parts 1 and 2, participants who discontinue due to a DLT during the DLT evaluation period, will be considered as DLT-evaluable participants. Participants who withdraw from the study during the DLT evaluation period for reasons other than a DLT may be replaced with a new participant at the same dose level. The incidence of DLT(s) during the DLT evaluation period will be used in dose escalation decisions and to define the BLRM-RD. AEs occurring after the DLT period will be considered for the purposes of defining the BLRM-RD upon agreement between the Sponsor, Medical Monitor (or designee), and investigators.

Participants experiencing a DLT will enter the safety follow-up period of the study. DLTs occurring after the 6-week DLT evaluation period for Part 1 will be accounted for in determining the BLRM-RD for the combination part.

A DLT is defined as one of the following and considered by the Investigator to be possibly, probably or definitely related to BMS-986277 and/or nivolumab.

AEs will be graded according to the NCI CTCAE v4.03, as listed below:

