**Table 2-2: On-Treatment Assessment Schedule (Monotherapy Dose Escalation - BMS-986277 [Part 1])(CA034001)**

Procedure a	Cycle 1 (42 days: 14 day lead-in period + 28 days) b				Cycle 2 (28 days) b				EOT c	Notes
	D1	D8 ( $\pm$ 3 days)	D15 d,e , D17 e , D19 e	D29 and D36 ( $\pm$ 3 days)	D1 ( $\pm$ 3 days)	D3 e and D5 e	D8 ( $\pm$ 3 days)	D15 and D22 ( $\pm$ 3 days)		
BMS-986277 Administration f	X		X		X	X				Participants will receive BMS-986277 at 1 of 4 different concentrations. Participants must be observed for at least 4 hours following the completion of BMS-986277 infusion due to the potential risk of and to monitor for infusion reactions. See Section 7.1.3.1 .

Abbreviations: AE = adverse event; C = cycle; CT = computed tomography; D = day; DLT = dose-limiting toxicity; ECG = electrocardiogram; ECOG = Eastern Cooperative Oncology Group; eCRF = electronic case report form; EOT = end of treatment; FU = follow-up; HCG = human chorionic gonadotropin; IMG = immunogenicity; IRT = interactive response technology; MRI = magnetic resonance imaging; PCWG3 = Prostate Cancer Clinical Working Group 3; PE = physical examination; PK = pharmacokinetic; Q4W = every 4 weeks; SAE = serious adverse event; SOC = standard of care; TNBC = triple-negative breast cancer; TSH = thyroid stimulating hormone; WOCBP = women of childbearing potential

- a Some of the assessments referred to in this section may not be captured as data in the eCRF. They are intended to be used as safety monitoring by the treating physician. Additional testing or assessments may be performed as clinically necessary or where required by institutional or local regulations.
- b Participants who complete the first cycle and do not have a DLT, have not had clinical evidence of disease progression, and are considered suitable for further treatment may receive up to 1 additional cycle of BMS-986277 with Cycle 2 beginning no sooner than 42 days after C1D1.
- c EOT visit is at C2D28 or at the time of study treatment discontinuation. If within 7 days prior to FU Visit 1, the EOT visit may be skipped and FU Visit 1 should be completed and include all EOT biomarker samples.
- d Up to + 7 day dosing for C1D15.

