### 2) Non-hepatic Non-hematological DLT

Any of the following events will be considered a non-hepatic non-hematological DLT:

- Any Grade 2 drug-related uveitis or eye pain or blurred vision that does not respond to topical therapy and does not improve to Grade 1 severity  $\leq 2$  weeks *or* requires systemic treatment.
- Grade 3 drug-related uveitis, pneumonitis, bronchospasm, neurologic toxicity, hypersensitivity reaction, or myocarditis, of any duration or infusion reaction not returning to baseline in  $< 1$  hour, will require discontinuation.

- Any Grade 3 or greater nondermatologic, nonhepatic nonhematological study treatment-related toxicity will be considered a DLT, with the following specific exceptions:
  - ◆ Grade 3 or Grade 4 electrolyte abnormalities that are not complicated by associated clinical adverse experiences, last less than 72 hours, and either resolve spontaneously or respond to conventional medical intervention
  - ◆ Grade 3 nausea, vomiting, or diarrhea that lasts less than 72 hours, and either resolves spontaneously or responds to conventional medical intervention
  - ◆ Isolated Grade 3 elevation of amylase or lipase not associated with clinical or radiographic evidence of pancreatitis
  - ◆ Isolated Grade 3 fever not associated with hemodynamic compromise (eg, hypotension, clinical or laboratory evidence of impaired end-organ perfusion or with other symptoms of infusion-related reactions that returns to  $\leq$  Grade 1 with standard treatment in  $\leq$  1 hour)
  - ◆ Grade 3 endocrinopathy that is well controlled by hormone replacement
  - ◆ Grade 3 tumor flare (defined as pain, irritation, or rash that localizes to sites of known or suspected tumor)
  - ◆ Grade 3 fatigue for  $\leq$  7 days
  - ◆ Grade 3 infusion reaction that returns to Grade 1 in  $\leq$  1 hour

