### 3) Dermatologic DLT

- Grade 3/4 rash if no improvement (ie, resolution to Grade  $\leq$  1) after a 1-week to 2-week infusion delay. Participants who have not experienced a Grade 3 drug-related skin AE may resume treatment in the presence of Grade 2 skin toxicity.
- Grade 4 rash of any duration

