## 7.4.2 Dose Delay Criteria for Study Treatment

Study treatment administration should be delayed for the following:

- Potential DLT, until DLT-relatedness is defined.
- Select AEs and laboratory abnormalities:
  - Grade  $\geq$  1 pneumonitis
  - Grade  $\geq$  2 abnormality in AST, ALT, or total bilirubin
  - Grade  $\geq$  2 abnormality in creatinine
  - Grade  $\geq$  2 diarrhea or colitis
  - Grade  $\geq$  2 neurological AE
  - AE, laboratory abnormality, or concurrent illness that, in the judgment of the investigator, warrants delaying study treatment administration.

- Criteria for participants who are required to permanently discontinue both study treatments are listed in [Section 8.1](#). Participants not meeting guidelines for permanent discontinuation will be permitted to resume therapy based on the criteria specified below in [Section 8.1.1](#). Participants eligible to resume study treatment will resume study treatment at the nominal treatment visit following their last received study treatment dose.

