### **7.4.3 Treatment Delays**

Participants who experience a potential DLT must have the study treatment held. Participants who are required to permanently discontinue both study treatments are listed in [Section 8.1](#). In addition, all Grade 2 hepatic, pulmonary, renal, gastrointestinal (GI), and neurological AEs should be evaluated and managed per the toxicity management algorithms ([Appendix 5](#)). Participants not meeting guidelines for permanent discontinuation will be permitted to resume study treatment based on the criteria specified below in [Section 8.1.1](#). Participants eligible to resume study treatment will resume study treatment at the visit following their last received dose.

If the reason for a dosing delay is not due to a potential DLT, then the DLT evaluation period may be extended to include at least 28 days after the start of the sequential doses in Part 1 or at least 14 days after the start of Cycle 2 Day 1 sequential doses in Part 2 to allow for adequate time to observe any potential DLTs following these sequential administrations.

Extensions to the period of dose delays may be granted for individual participants on a case-by-case basis after specific consultation and agreement between the investigator and BMS Medical Monitor (or designee) in settings where benefit/risk may justify continued study treatment (eg, participant deriving clinical benefit who requires prolonged steroid taper for the management of non-DLT drug-related AEs or experiences delays for the management of a nondrug-related AE).

The tumor assessments (ie, CT/MRI, positron emission tomography [PET], etc) will continue relative to the participant's first dose as outlined in [Section 2](#) (Schedule of Activities) regardless of any treatment delay incurred.

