## APPENDIX 9 STATISTICAL METHODOLOGY

### STATISTICAL DETAILS FOR BAYESIAN LOGISTIC REGRESSION MODEL (BLRM AND BLRM-COPULA) TO GUIDE DOSE ESCALATION AND BASKET DESIGNS TO ASSESS HOMOGENEITY AND FUTILITY IN COHORT EXPANSION

#### 1 MODEL SETUP FOR BMS-986277 MONOTHERAPY

##### 1.1 Methodology Description for Monotherapy

An adaptive 2-parameter Bayesian Logistic Regression Model (BLRM) guided by the escalation with overdose control (EWOC) principle will be used to guide the dose escalation of BMS-986277 monotherapy in the monotherapy phase, providing dose recommendations during dose escalation.

The BLRM will be fitted on the dose-limiting toxicity (DLT) data during the first 6 weeks of treatment accumulated throughout the dose escalation to model the dose-toxicity relationship of BMS-986277 in the monotherapy dose escalation phase.

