#### 7.1.2 Post-Baseline Period

- On-treatment period for evaluation of AEs and measurements (including laboratory tests) post baseline is defined as on or after the first dose of study treatment up to and including 30 days or 100 days after the last dose of study treatment for participants who are off study treatment, for Part 1 and Parts 2-3, respectively. For participants who are still on study treatment, the entire post-baseline period will be counted as on-treatment.
- Primary analysis of safety endpoints will be based on the treatment period.
- DLTs will be evaluated during the 42-day DLT period.

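### The DLT window for a participant whose virus dosing slips is optional, withheld for potential-DLT holds, and not matched by the six weeks in Appendix 9

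*Protocol*

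**What the plan says.** Section 7.4.1 of the protocol sets the DLT evaluation period at 42 days. It then says: "In the event of dose delays for reasons other than a potential DLT, the DLT evaluation period may be extended", so as to include at least 28 days from the start of the sequential doses in Part 1, or at least 14 days from Cycle 2 Day 1 in Part 2. Section 7.4.3 repeats the limit: "If the reason for a dosing delay is not due to a potential DLT, then the DLT evaluation period may be extended". The synopsis allows an extension for dose delays without naming a reason. Section 5.1.1 allows it for non-DLT delays.

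Dosing can slip in ordinary ways:
- Part 1: Table 2-2, footnote d, reads "Up to + 7 day dosing for C1D15".
- Part 2: Section 8.1.1 lets Cycle 2 virus start as late as Day 36 when adverse events persist.
- Either part: Section 7.4.2 requires a hold for a "Potential DLT, until DLT-relatedness is defined". Some DLT definitions take time to settle. Grade 3 rash is judged "after a 1-week to 2-week infusion delay". One ocular definition, which begins "Any Grade 2 drug-related uveitis or eye pain or blurred vision that does not respond to topical therapy", allows two weeks for improvement.

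On what enters the Part 1 model, Appendix 9, 1.1 says: "The BLRM will be fitted on the dose-limiting toxicity (DLT) data during the first 6 weeks of treatment". Section 10.1.1.1 and Appendix 9, 2.1 instead refer to the DLT period, with no number of weeks. SAP 7.1.2 says: "DLTs will be evaluated during the 42-day DLT period".

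Replacement is optional for delays over 7 days (7.4.1) and for participants not evaluable for DLT (7.2).

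**The concern.** The 42 days have a purpose. Section 5.1.1 builds them from two weeks after a single infusion plus the period that covers repeat dosing. When the repeat doses move and the end of the window does not, the days lost are those after repeat dosing.

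Two features of the text allow this. The extension is permitted but not required, and no one is named to decide it. It is also withheld when the delay was due to a potential DLT. That makes sense if the event proves to be a DLT, because it is then counted. It does not make sense if the event is cleared: the participant goes back on drug with a shortened observation period and, under 7.4.1 and 7.4.3, no extension. Such a participant has just had a suspected toxicity and is a poor candidate for shorter follow-up.

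If the window is extended, a DLT between Day 43 and its new end falls inside the 7.4.1 period but outside the six weeks in Appendix 9. The study is open-label, so whether to extend, count or replace could be settled after the outcome is known. The decision at stake is whether the next cohort receives a given dose in a first-in-human escalation.

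**Working it through.** **Step 1. Days observed if the window closes on Day 42 (inclusive counts).**

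| Case | Start | Planned | Left by Day 42 | Full period would end |
|---|---|---|---|---|
| Part 1, on schedule | Day 15 | 28 | 42 − 15 + 1 = 28 | Day 42 |
| Part 1, +7-day window | Day 22 | 28 | 42 − 22 + 1 = 21 | Day 49 |
| Part 1, 14-day hold, event cleared | Day 29 | 28 | 42 − 29 + 1 = 14 | Day 56 |
| Part 2, on schedule | Day 29 | 14 | 42 − 29 + 1 = 14 | Day 42 |
| Part 2, C2D1 delayed (8.1.1) | Day 36 | 14 | 42 − 36 + 1 = 7 | Day 49 |

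The 7-day rescheduling limit in 7.1.3.1 is for non-toxicity reasons, so it does not prevent the third row.

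**Step 2. Reproduce the protocol's worked example.** Inputs are from Appendix 9, Table 2 and 2.2: log(α) and log(β) are bivariate normal with means −0.959 and 0.884, SDs 1.005 and 1.240, and correlation 0.055. I used the standard two-parameter form, logit(p) = log(α) + β·log(dose / 3×10^12), integrated on a grid. With 0/3 at 3×10^10 and 1/3 at 3×10^11:
- target probability at the three lower doses: 0.068, 0.257, 0.415 (protocol: 0.068, 0.254, 0.418)
- overdose probability at 3×10^12: 0.561 (protocol: 0.579)

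Agreement is within 0.02. Grid spacing moves the results below by about 0.003 at most.

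**Step 3. Leave out or count one late DLT at 3×10^12 vp, with 0/3 at each lower dose.** The cap on P(DLT rate ≥ 33%) is 0.35.

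| Left out | P(≥33%) | Counted | P(≥33%) | Crosses cap? |
|---|---|---|---|---|
| 0/3 | 0.13 | 1/3 | 0.37 | yes, narrowly |
| 1/6 | 0.165 | 2/6 | 0.386 | yes |
| 2/9 | 0.195 | 3/9 | 0.399 | yes |
| 0/6 | 0.046 | 1/6 | 0.165 | no, both allowed |
| 2/6 | 0.386 | 3/6 | above 0.64 | no, both barred |

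At 2/9 the target probability is 0.555, above the 0.50 required. The dose then meets every condition for the model-recommended dose if the late event is omitted, and fails overdose control if it is counted. The protocol's own example (Appendix 9, 3.1) shows the same sensitivity one level down: at 1×10^12 vp, 0/3 escalates and 1/3 stays.

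Counting a briefly observed DLT-free participant also matters. 1/4 gives 0.286 but 1/3 gives 0.37; 2/7 gives 0.311 but 2/6 gives 0.386.

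**Step 4. How often a DLT would fall late.** The documents give no timing distribution, so this is a range.
- If a 33% risk is spread evenly over the 28 days, a Day 42 cut sees 1 − 0.67^(21/28) = 25.9% (start on Day 22) or 1 − 0.67^(14/28) = 18.1% (start on Day 29).
- If toxicity follows infusion promptly, the loss is near zero. Both enadenotucirev monotherapy DLTs came after the first dose (Appendix 9, 1.2.1).

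The Part 2 copula formula is redacted, so the model effect is shown for Part 1 only.

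**The case against.** The best defence is that the documents, read together, already give the answer. Section 7.4.1 defines the period with its extension and says that DLTs in that period drive escalation. Section 10.1.1.1 and Appendix 9, 2.1 tie the model to that period. On this reading, the six weeks in Appendix 9, 1.1 are shorthand for the nominal length, and a DLT on Day 45 of an extended window enters the model. That reading is reasonable, and a reader should not infer that such an event must be excluded. But 7.4.1 itself later speaks of the six-week period for Part 1, and the reading does not make the extension mandatory. Appendix 9's Part 2 text names no number of weeks, so this mismatch concerns Part 1.

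Similarly, a cleared event can be called a non-DLT delay under 5.1.1, and the synopsis has no exclusion. Sections 7.4.1 and 7.4.3, however, exclude delays due to a *potential* DLT, and those are the operative rules.

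Other stronger inferences are not supported:
- *The SAP contradicts the current protocol.* SAP version 1.0 incorporates changes only up to Revised Protocol 03, and Revised Protocol 05 updated both the DLT and delay sections. The fixed 42 days may simply be out of date.
- *Late DLTs are ignored.* Section 7.4.1 lets later events bear on the recommended dose by agreement and carries late Part 1 DLTs into the combination decision. SAP 8.6.1 tabulates DLTs outside the window.
- *A routine Part 1 slip halves the observation.* It leaves 75% (21/28). Half needs a 14-day hold, and replacement is then allowed.
- *Cycle 2 may start inside an extended window.* Day 42 is a floor. Participants must also complete the first cycle, which can be read as covering the extra days.

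**Conclusion.** The point holds as an inconsistency in the current protocol that should be removed. It does not invalidate the escalation design. Followed literally, the text lets a Part 1 participant count as DLT-free after 21 or 14 of the 28 intended days, and a Part 2 participant after 7 of 14. It also leaves unclear whether a DLT on Days 43 to 49 enters the Part 1 model. That choice can move overdose probability across 0.35 in plausible patterns (1/6 against 2/6; 2/9 against 3/9), though not in all.

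The size rests on three assumptions: the Table 2 prior, no DLTs at lower doses, and a DLT actually occurring late. The 1/3 result lies about as far from the cap as my calculation lies from the protocol's example, so less weight belongs on it. If toxicity is prompt, the practical effect is small. The existing safeguards are optional or act after the Part 1 model, and none fixes its input.

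**What to change.** Use one definition in protocol 5.1.1, 7.4.1, 7.4.3 and Appendix 9, 1.1, and in SAP 7.1.2 when the SAP is brought up to the current protocol:

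- The DLT period runs from C1D1 to the later of Day 42 and 28 days after the actual D15 infusion (Part 1) or 14 days after the actual C2D1 infusion (Part 2). This applies to any delay, including a hold for a potential DLT later judged not to be one.
- The BLRM uses DLTs in this window.
- Change 'may be extended' to 'will be extended', and delete the clause that limits extension to delays not caused by a potential DLT.
- Cap the extension at a 14-day delay, because 8.1 allows gaps of up to six weeks. A DLT-free participant with a longer delay, or who does not complete the window, is not DLT-evaluable and is replaced. This supersedes the optional replacement rule for delays over 7 days.

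Cost: a wording amendment. A dose decision waits up to 7 days longer when D15 falls on Day 22 or C2D1 on Day 36 (49 − 42), and up to 14 days after a 14-day hold (56 − 42). An occasional replacement participant may be needed.

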### **7.4.4 Exceptions to Permanent Discontinuation Criteria**

Detailed exceptions to permanent discontinuation are listed in [Section 8.1](#).

Any drug-related AE occurring at any time that meets DLT criteria as outlined in [Section 7.4.1](#) will require permanent discontinuation except in cases of non-life-threatening AEs that meet DLT criteria and that have been resolved to Grade 1 or baseline. In these specific cases consideration to resume treatment will be made on a case-by-case basis in a discussion between the investigator and BMS Medical Monitor (or designee), taking into account the overall benefit/risk ratio for the individual participant and considering the following factors:

- A 2-week washout period is required after completing the immune suppressive treatment used to manage the AE (eg, steroids). The AE should not recur/worsen during the washout period.
- Evidence for clinical or radiographic benefit must be present, which can include improvement of physical symptoms (eg, ECOG status, shortness of breath), symptomatic improvement in combination with assessment of SD, or radiographic response.

In the event of recurrence of the AE that met the DLT criteria, study therapy will be permanently discontinued for the participant.

Additionally, consideration to permanently discontinue study therapy for participants with any severe Grade 3 drug-related AE that recurs will be made on a case-by-case basis in a discussion between the investigator and BMS Medical Monitor (or designee).

All participants who discontinue treatment should comply with protocol-specified follow-up procedures as outlined in [Sections 2](#) (Schedule of Activities) and [5.1.5](#). The only exception to this requirement is when a participant withdraws consent for all study procedures including post-treatment study follow-up or loses the ability to consent freely (eg, imprisonment or involuntarily incarceration for the treatment of either a psychiatric or physical illness).

If study treatment is discontinued prior to the participant's completion of the study, the reason for the discontinuation must be documented in the participant's medical records and entered on the appropriate Case Report Form (CRF) page.

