## **8 DISCONTINUATION CRITERIA**

### **8.1 Discontinuation from Study Treatment**

Participants MUST discontinue investigational product (and non-investigational product at the discretion of the investigator) for any of the following reasons:

- Participant's request to stop study treatment. Participants who request to discontinue study treatment will remain in the study and must continue to be followed for protocol specified follow-up procedures. The only exception to this is when a participant specifically withdraws consent for any further contact with him/her or persons previously authorized by participant to provide this information
- Any clinical AE, laboratory abnormality or intercurrent illness which, in the opinion of the investigator, indicates that continued participation in the study is not in the best interest of the participant
- Termination of the study by Bristol-Myers Squibb (BMS)
- Loss of ability to freely provide consent through imprisonment or involuntarily incarceration for treatment of either a psychiatric or physical (eg, infectious disease) illness. (Note: Under specific circumstances, a participant who has been imprisoned may be permitted to continue as a participant. Strict conditions apply and BMS approval is required.)
- Pregnancy

- Documented and confirmed disease progression as defined by RECIST v1.1 or PCWG3 (Appendix 7 and 8, respectively) unless participants meet criteria for treatment beyond progression (Section 8.1.2)
  - Clinical deterioration while receiving active study treatment that, in the opinion of the investigator, indicates that continued participation in the study is not in the best interest of the participant
  - Discretion of the investigator
  - Inability to comply with the protocol requirements
  - Individual participants with confirmed CR will be given the option to discontinue study treatment on a case-by-case basis after specific consultation and agreement between the investigator and BMS Medical Monitor (or designee) in settings where benefit/risk justifies discontinuation of study treatment
  - Any drug-related AE occurring at any time that meets DLT criteria as outlined in Section 7.4.1 will require permanent discontinuation except in cases of non-life-threatening AEs that meet DLT criteria and that have been resolved to Grade 1 or baseline. See Section 8.1.1 for considerations regarding resuming treatment.

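### The rules for stopping and resuming treatment after a DLT disagree across Protocol Sections 7.4.1, 7.4.4, 8.1 and 8.1.1

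*Protocol*

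**What the plan says.** **Protocol Section 7.4.1** states that DLTs "will require permanent discontinuation for all study participants regardless of treatment cycle". It adds: "Participants experiencing a DLT will enter the safety follow-up period of the study". It also offers a second BMS-986277 cycle, in all study parts, only to participants who finish the first cycle without a DLT. None of these statements refers to an exception.

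**Protocol Section 7.4.4** says that a drug-related AE meeting the DLT criteria "will require permanent discontinuation except in cases of non-life-threatening AEs that meet DLT criteria and that have been resolved to Grade 1 or baseline". Resumption is then decided case by case with the Medical Monitor. Two factors are listed: "A 2-week washout period is required after completing the immune suppressive treatment used to manage the AE", and "Evidence for clinical or radiographic benefit must be present".

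**Protocol Section 8.1** opens with "Participants MUST discontinue investigational product (and non-investigational product at the discretion of the investigator) for any of the following reasons". Its DLT bullet reads "Any drug-related AE occurring at any time that meets DLT criteria as outlined in Section 7.4.1 will require permanent discontinuation", repeats the 7.4.4 exception, and ends with "See Section 8.1.1 for considerations regarding resuming treatment". Later bullets in the same section give separate allowances for certain Grade 3 and Grade 4 events, some of which are DLTs under 7.4.1.

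**Protocol Section 8.1.1** sets the general resumption rule (return to Grade 1 or below, or to baseline). It also lets participants with endocrinopathies controlled on hormone replacement resume after consulting the Medical Monitor.

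**The concern.** A site facing a DLT has to know whether re-dosing is barred, allowed under the conditions in 7.4.4, or allowed under a lighter rule in 8.1. For some events the protocol supports more than one of these answers. Two sites could then treat the same event differently, each with text to cite. In a first-in-human study of a replicating virus combined with a checkpoint inhibitor, what is at stake is re-dosing safety and consistent conduct. Section 9 does not allow protocol waivers or exemptions, so the inconsistency has to be settled in the text.

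**Working it through.** No arithmetic is involved beyond one interval check and one dose count. The check sets the DLT definitions in 7.4.1 against the stopping and resuming rules.

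**1. General rule against exception.** Section 7.4.1: every DLT stops permanently and goes to safety follow-up. Sections 7.4.4 and 8.1: the same, except for non-life-threatening DLTs resolved to Grade 1 or baseline. Section 7.4.4 is headed as a list of exceptions and names 7.4.1, so the two can be read as rule and exception. What is missing is the link from 7.4.1. The no-DLT condition for Cycle 2 is also unlinked, so a participant cleared under 7.4.4 still fails it as written.

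**2. Events that are DLTs in 7.4.1 but have an allowance in 8.1.**

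| Event | Section 7.4.1 | Section 8.1 / 8.1.1 | Result |
|---|---|---|---|
| Controlled Grade 4 endocrinopathy, not adrenal insufficiency | DLT; only well-controlled Grade 3 is excepted | May continue if resolved or controlled, with Medical Monitor approval; 8.1.1 lets controlled cases resume | Conflict when controlled but unresolved |
| Grade 4 neutropenia | DLT at 5 days or more | Waived at 5 days or less | Conflict at exactly 5 days |
| Asymptomatic Grade 4 amylase or lipase | DLT; only isolated Grade 3 is excepted | Discontinuation not required | Can be reconciled, but not stated |
| Grade 3 AST or ALT | DLT | Stopping is the default; continuation possible after Medical Monitor discussion | Can be reconciled, but not stated |

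*Endocrinopathy.* The DLT bullet in 8.1 allows resumption only after resolution to Grade 1 or baseline. The Grade 4 allowance and 8.1.1 accept control on replacement therapy instead. If the DLT bullet prevails, the controlled-but-unresolved half of the allowance has almost nothing left to cover. If the allowance prevails, the DLT bullet is overridden.

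*Neutropenia.* {duration ≥ 5 days} ∩ {duration ≤ 5 days} = {5 days}. With the waiver at < 5 days, the intersection is empty.

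*Amylase/lipase and AST/ALT.* The Grade 4 bullet and the AST/ALT sub-bullet are separate bars that lack the resolved-DLT exception. The allowances can be read as lifting those bars and leaving the DLT bullet in control, so that 7.4.4 governs.

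**3. The pointer.** The DLT bullet sends the reader to 8.1.1 only. That section has neither the washout after immune suppression nor the evidence-of-benefit condition; both are in 7.4.4.

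**4. What re-dosing is left open.** A first-cycle DLT fails the condition for Cycle 2 virus. Within a cycle, at most 4 − 1 = 3 virus doses remain after a first dose in Part 1 Cycle 1 (Days 1, 15, 17, 19), and 3 − 1 = 2 in any other cycle. The 7-day limits on sequential doses narrow this further. Nivolumab, at up to 26 cycles, is assessed separately under 8.1.

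**The case against.** The strongest case on the other side is that this is mostly drafting. Section 7.4.4 is plainly the exception to 7.4.1, and 8.1 repeats it. The bullets in 8.1 are separate triggers, so an allowance under one does not cancel another. Safeguards surround the gap: treatment is held for a potential DLT (7.4.2, 7.4.3), and the endocrinopathy allowance needs Medical Monitor approval. The AST/ALT footnote requires a discussion with the Medical Monitor. In combination therapy, Cycle 2 virus may slip by at most 7 days for persisting AEs.

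Much of this stands, and it rules out several stronger readings that a reader might infer:

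- *That 8.1 contradicts 7.4.1 outright on all four events.* It does so on two. For amylase/lipase and AST/ALT the separate-trigger reading gives the allowances a real function and leaves 7.4.4 in control. The remaining fault there is silence on precedence.
- *That the reference to 8.1.1 is circular*, because 8.1.1 excludes participants who meet permanent discontinuation criteria. It is not. The DLT bullet excepts resolved non-life-threatening DLTs from those criteria, so these participants do reach 8.1.1. The pointer is incomplete.
- *That a participant with a first-cycle DLT could receive Cycle 2 virus under the 8.1 allowances.* The no-DLT condition in 7.4.1 bars it as written.

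The objection does not remove the unlinked absolute wording in 7.4.1, the unresolved endocrinopathy case, or the 5-day overlap.

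**Conclusion.** The stopping and resuming rules are inconsistent as written and should be corrected, but the problem is limited. There is one missing exception in 7.4.1, with an unaligned Cycle 2 condition. Two events have contradictory rules: controlled but unresolved Grade 4 endocrinopathy, and Grade 4 neutropenia at a single duration. Two further events have no stated order of precedence, and one pointer is incomplete. The list of events is not claimed to be complete.

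The practical exposure is mainly remaining within-cycle virus doses and nivolumab. The documents give no expected rate for these events, and 7.4.1 does not say which drug stops, so no count of affected participants is offered. A reader might infer that dose escalation is affected. It is not: an event is a DLT under 7.4.1 whatever happens to treatment afterwards, so the BLRM inputs stay the same while the definitions stand.

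The conclusion assumes that each event is treatment-related with no clear alternative cause, as 7.4.1 requires. It also assumes that a Grade 4 event is not automatically life-threatening in the sense of Appendix 3. If it were, the 7.4.4 route would be closed to Grade 4 events, and the allowances in 8.1 would be harder to reconcile.

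**What to change.** 1. **Section 7.4.1:** add *except as provided in Section 7.4.4* to the permanent-discontinuation sentence and to the safety follow-up sentence. State whether the no-DLT condition for Cycle 2 still applies to participants cleared under 7.4.4, and align the matching statements in Sections 2 and 5.1.1 to 5.1.3 if it changes.
2. **Section 8.1, Grade 3 and Grade 4 allowances:** state that these and the AST/ALT footnote do not override the DLT bullet, so an event meeting DLT criteria resumes only under 7.4.4. If the team intends controlled Grade 4 endocrinopathy to continue, add it to the DLT exceptions in 7.4.1 instead.
3. **Section 8.1, Grade 4 neutropenia:** change the waiver to less than 5 days.
4. **Section 8.1, DLT bullet:** write *See Sections 7.4.4 and 8.1.1*.

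The cost is protocol wording only, with no change to visits, sample size or analysis. The one exception is the alternative in item 2: moving an event into the 7.4.1 exceptions changes its DLT classification, and so the data that feed the escalation model.
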